6.4 Handling of Missing Data

All attempts will be made to limit the amount of missing data. Unless otherwise specified, missing data will be handled by multiple imputation for the primary endpoint (SSQ12) with covariates of gender, age and baseline in the ITT Analyses. For all other analyses, no attempt will be made to impute missing data, and the number of observations available will be reported so the reader can assess the impact of missing data.

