9.3.2 Randomization

The design of the clinical investigation is a prospective, 1:1 randomized clinical trial. The intervention arm to which a participant is assigned is determined by an allocation schedule developed by [REDACTED]

To ensure balance between the treatment arms, participants will be randomized as described in the Statistical Analysis Plan (D1309522). Block size will not be revealed to field center staff as this would allow them to determine the final treatment assignment of a block before ascertaining eligibility and obtaining consent. The randomization will be maintained by the sponsor within a data management system. Randomization will be performed at POV1.

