9.3.5 Preoperative Visit 2 (POV2) - Baseline

Preoperative visit 2 (POV2) baseline will occur 4-6 weeks post POV1 (+/- 2 weeks) to enable scheduling of surgery for Arm A subjects. Both Arm A and Arm B subjects will complete POV2 with appropriately fit hearing aids and glasses (if required). The full neuropsychological battery in addition to the audiology, psychosocial, physical, and quality of life metrics will be completed as described in Section 9.2. Speech recognition will be assessed in the everyday listening condition (aided bilaterally) and the ear to be implanted listening conditions with the contralateral ear plugged. Datalogs will be retrieved for the hearing aid.

Medical history will be completed minimally via the ACE 27 index. The Investigator or appropriately delegated staff may add additional otologic history (hearing history) which they deem relevant to the study.

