3.2 Secondary Objective

To assess cognition in older adults with hearing loss with a Cogstate® battery of neuropsychological tests.

Statistical Analysis Plan		Page 7 of 16
Sponsor Cochlear	Study Hearing Loss in Older Adults	CIP Version 9.0

4 Study Design

Prospective, 1:1 randomized controlled trial of immediate versus delayed cochlear implantation (CI) on hearing satisfaction, handicap, communicative function, loneliness, mental wellbeing, quality of life and cognitive functioning. The study will contain approximately 60 subjects, with a minimum of 28 subjects in each arm.

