4.1 Randomization

Subjects will be randomized after eligibility has been confirmed and confirmed that the subject will participate in the clinical investigation. Randomization will be performed using a random permuted block design stratified by field site with a 1:1 allocation ratio (Arm A: immediate cochlear implant vs. Arm B: hearing aid control). If a subject withdraws from the clinical investigation, they will be not be replaced by another subject. The randomization table will account for 20% subject attrition.

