5.1.1 Primary endpoint

The primary endpoint for the clinical investigation is assessment of the impact of cochlear implantation versus continued hearing aid use on the Speech, Spatial and Qualities of Hearing – short form (SSQ12) test measure at Follow-up Visit 1 (FUV1). Each subject will serve as their own control.

Data from a clinical investigation on the Cognitive Performance of Severely Hearing-impaired Older Adults Before and After Cochlear Implantation (1) was used to estimate the effect of cochlear implantation on the SSQ12.

The sample size estimation for the primary endpoint is based on the mean (SD) change of 3.0 (1.8) for the change in SSQ12 score reported in Claes et al. (pre-operative to postoperatively at six months post-activation) (1). The sample size estimation assumes that the observed mean change and standard deviation of change reported by Claes for SSQ12 is representative of the corresponding values for the clinical population under investigation.

Statistical Analysis Plan		Page 8 of 16
Sponsor Cochlear	Study Hearing Loss in Older Adults	CIP Version 9.0

Sample size calculations were conducted using PASS statistical software under the following general assumptions:

1. Two-sample t-test
2. Two-sided 0.025 α levels
3. 80% power
4. No accounting for attrition or lost to follow up

In order to achieve 80% power with an effect size of 1.667 ($d = (\mu_A - \mu_B)/\sigma$) with 20% attrition, a sample size of 12 per arm would be needed respectively. Therefore, a sample size of 60 supports the effect sizes observed in Claes et al. (2018) as well as possible attrition.

6 Statistical Analyses

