6.2 Analysis Populations

The following analysis populations are defined for analysis:

- Enrolled Analysis Set:** The enrolled population will consist of all subjects who signed an informed consent form and have been included into the study database.
- Intention-to-treat Analysis Set:** The intention-to-treat (ITT) population consists of all enrolled subjects who were subsequently randomized. The ITT set will be analyzed according to randomized treatment assignment regardless of adherence to treatment protocol (e.g. dropout/withdrawal or CIP deviations).
- Safety Analysis Set:** The safety population will consist of all ITT subjects who received the device and will be analyzed according to treatment actually received (e.g. this is an as-treated analysis set). If all patients receive study treatment according to randomization, the safety set will be identical to the ITT set.

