6.6.1.1 Primary Analysis

The primary efficacy endpoint will be assessed with the following hypothesis:

$$H_0: \mu_A \geq \mu_B$$

$$H_a: \mu_A < \mu_B$$

Statistical Analysis Plan		Page 11 of 16
Sponsor Cochlear	Study Hearing Loss in Older Adults	CIP Version 9.0

Where μ_{A6} is the mean SSQ12 score for the cochlear implantation treatment Arm A and μ_{B6} is the mean SSQ12 score for the hearing aid control Arm B at FUV1. The hypothesis will be evaluated using a regression model with treatment and baseline score as covariates. Significance of the treatment effect will be assessed by the p-value for the treatment arm from the regression model.

For analyses using means in the primary endpoints, where there is evidence the model assumptions are not met (e.g. lack of normality of the residuals), transformations or non-parametric tests will be employed.

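### The multiple imputation of SSQ12 leaves out treatment arm, so the primary effect estimate shrinks by about the missing fraction if data are missing at random within arm

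*SAP*

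**What the plan says.** SAP 6.4 gives the missing-data rule for the primary endpoint: "missing data will be handled by multiple imputation for the primary endpoint (SSQ12) with covariates of gender, age and baseline in the ITT Analyses". The list has three variables and arm is not one of them. Nothing elsewhere in the SAP or protocol adds arm or says that imputation is done separately by arm.

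SAP 6.6.1.1 tests the primary hypothesis "using a regression model with treatment and baseline score as covariates" and takes the result from the treatment term. The SAP therefore counts treatment as a covariate in the analysis model but not in the imputation model.

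Imputed values will enter the primary result, because SAP 6.2 has the ITT set "analyzed according to randomized treatment assignment regardless of adherence to treatment protocol", dropouts included. On the amount of missing data there are two indications: "The randomization table will account for 20% subject attrition" (SAP 4.1), and a planned size of "approximately 60 subjects, with a minimum of 28 subjects in each arm" (SAP section 4).

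On timing, protocol 9.3.2 says "Randomization will be performed at POV1". The baseline visit "will occur 4-6 weeks post POV1 (+/- 2 weeks) to enable scheduling of surgery for Arm A subjects" (protocol 9.3.5), and protocol 9.3.6 places Arm A surgery one week after that. Before visit windows, surgery is thus 5 to 7 weeks after randomization.

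**The concern.** An imputation model should contain every variable in the analysis model, above all the one whose coefficient is the result. If arm is left out, a missing Arm A score and a missing Arm B score with the same baseline, age and gender are drawn from the same distribution, which lies between the two arms. Imputed Arm A values are pulled down and imputed Arm B values pulled up (taking Arm A as the better arm), so the estimated difference moves toward zero.

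The standard error is affected too. The pooled imputation model absorbs the arm difference into its residual, so imputed values are too scattered. Rubin's rules also give no credit for the no-difference assumption built into the imputations.

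At stake are the size of the reported SSQ12 benefit and its confidence interval. The trial is unblinded (SAP 4.2), so adding arm once data have been seen would be an unplanned change to the primary analysis in the direction of a larger effect.

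**Working it through.** **1. The plan's own figure.** SAP 5.1.1 uses a "mean (SD) change of 3.0 (1.8) for the change in SSQ12 score". The standardized effect is 3.0/1.8 = 1.667. An exact two-sample t-test at two-sided 0.025 and 80% power needs 9 per arm (power 84.4%). Allowing for 20% attrition, 9/0.8 = 11.25, rounded up to 12 per arm, as the SAP states.

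**2. Expected shrinkage.** Let mA and mB be the missing fractions in the two arms and δ the true difference, with data missing at random within arm. The pooled model centres imputed values at a fraction p = (1−mA)/(2−mA−mB) of the distance from the Arm B mean to the Arm A mean. The completed-data difference is then δ[(1−mA) + (mA−mB)p], so the proportional shrinkage is

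[mA(1−mB) + mB(1−mA)] / (2−mA−mB),

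which equals m when mA = mB = m.

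For δ = 3.0:
- 2/30 missing per arm (6.7%): 3.0 × (28/30) = 2.80
- 10% per arm: 3.0 × 0.90 = 2.70
- 20% per arm: 3.0 × 0.80 = 2.40
- 30% in one arm and 10% in the other: shrinkage (0.27 + 0.07)/1.6 = 0.2125, giving 2.36
- 40% in one arm and none in the other: shrinkage 0.4/1.6 = 0.25, giving 2.25

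**3. Excess scatter.** With score SD 1.8 and an assumed baseline correlation of 0.5, the within-arm residual variance is 1.8² × 0.75 = 2.43 (SD 1.56). The pooled model adds about δ²/4 = 2.25, for a total of 4.68 (SD 2.16).

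**4. Simulation.** Set-up: 30 per arm, proper normal imputation with 20 imputations, Rubin's rules with small-sample degrees of freedom, FUV1 SSQ12 regressed on arm and baseline, and 1,500 trials per scenario (2,000 at effect 1.5; 4,000 under the null). The SAP's 3.0 and 1.8 describe a pre-to-post change. Using them as a between-arm difference and a score SD is an assumption, as is the correlation of 0.5.

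True difference 3.0; estimate (mean SE; empirical SD):

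| Missing per arm | As written | Arm added | CI width, as written v arm added | Coverage |
|---|---|---|---|---|
| 2/30 (7%) | 2.78 (0.46; 0.40) | 2.99 (0.42; 0.43) | 1.85 v 1.69 (9% wider) | near 95% |
| 3/30 (10%) | 2.70 (0.48; 0.40) | 3.01 (0.43; 0.44) | 1.95 v 1.74 (12% wider) | near 95% |
| 6/30 (20%) | 2.38 (0.55; 0.39) | 2.99 (0.46; 0.47) | 2.23 v 1.87 (19% wider) | 87% v 94% |

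Rejection rates, as written v arm added:

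| Missing per arm | No effect | Effect 1.5 (illustrative) |
|---|---|---|
| 7% | 3.7% v 5.3% | 90% v 93% |
| 10% | 2.7% v 4.8% | 88% v 93% |
| 20% | 1.7% v 4.8% | 73% v 88% |

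At effect 3.0, power is at least 99.9% either way. At 20% missing the as-written estimate stays at 2.38 with correlation 0.3 or 0.7, and with SD 2.2. With missingness of 30% and 10%, in either order, it is 2.35. Repeat runs with gender and age in the imputation model gave 2.80 at 7% missing and 2.38 at 20%.

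**5. Arm A subjects who withdraw before surgery.** Assume no effect without an implant. If k of 30 are never implanted, the true ITT difference is 3.0 × (1 − k/30).

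| Missing per arm; never implanted in Arm A | True ITT | As written | Arm added | Arm added, never-implanted imputed from control arm |
|---|---|---|---|---|
| 6; 2 | 2.80 | 2.39 | 3.00 | 2.80 |
| 6; 6 | 2.40 | 2.38 | 2.99 | 2.39 |
| 2; 1 | 2.90 | 2.81 | 3.01 | 2.91 |

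**The case against.** **The text is silent rather than wrong.** SAP 6.4 does not say that arms are pooled, and a careful statistician might impute by arm anyway. That is possible, but the section gives an explicit covariate list, and programming that list omits arm. A primary analysis should not depend on the programmer departing from it.

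**The consequence is small.** This largely stands. The bias is conservative, significance at the planning effect is unaffected, and the larger harms need 20% missing FUV1 scores. The 20% in SAP 4.1 is an attrition allowance, not a forecast. If the 28 per arm means evaluable subjects (an assumption), about 7% would be missing, and the bias is about 0.2 points with coverage near 95%.

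**Adding arm can overstate the benefit.** This is the strongest point. If all six missing Arm A subjects were never implanted, the as-written estimate is almost right (2.38 against 2.40, coverage 99.5%), while adding arm gives 2.99 with 76% coverage. With two of six, adding arm overstates by 0.20 (94% coverage) and the as-written model understates by 0.41 (96%). Pooled imputation is therefore right only by accident. Imputing the never-implanted subjects from the control arm recovers the truth in both cases, so adding arm should be paired with that sensitivity analysis.

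**The documents complicate who is affected.** SAP section 2 ties enrolment to implantation, while SAP 6.2 defines the enrolled set by consent and database entry. The 6.2 definition governs the ITT set, which takes enrolled subjects who were subsequently randomized, so an unimplanted randomized subject remains in it. Separately, SSQ12 is first collected at POV2, after randomization, so a subject lost in between has no baseline score. That gap is real, but it affects the current wording just as much.

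**Conclusion.** The concern holds and should be fixed. The imputation model as written omits the variable that the primary analysis estimates. If data are missing at random within arm, the SSQ12 difference is understated by about the missing fraction: roughly 0.2 points of 3.0 at 7% missing, 0.3 at 10% and 0.6 at 20%. The interval is 9%, 12% and 19% wider than it should be. Type I error is not inflated, and the test result at the planning effect hardly changes. A material loss of power needs both substantial missing data and a true effect well below plan, for example 73% against 88% at an effect of 1.5 with 20% missing.

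The shrinkage depends on the missing-at-random assumption, which the SAP does not state. The interval, coverage and power figures also depend on the assumed score SD and correlation. If the missing Arm A subjects are mainly people who were never implanted, the as-written estimate can fall close to the true ITT difference.

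**What to change.** In SAP 6.4, change the imputation covariates to *randomized treatment arm, gender, age and baseline SSQ12*, or state that imputation is done separately by arm. Site is not needed for consistency with the primary model, which does not contain it.

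Add a sentence saying that the imputation assumes data are missing at random within arm. It would be sensible to say in the same place how a missing baseline SSQ12 is handled.

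Add a sensitivity analysis, to be run if any Arm A subject withdraws before surgery, that imputes those subjects from the control-arm distribution.

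The cost is two or three sentences in the SAP, one more variable in the imputation code and one conditional run. No additional data are needed.

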Ancillary analyses	
Ancillary analyses include:
 
 Investigating treatment effect on neuropsychological measures using the Hearing Impaired Montreal Cognitive Assessment (HI-MoCA) at Follow-Up Visit 1 (FUV1). Investigate the treatment effect of immediate cochlear implantation vs continued use of HAs on psychosocial measures such as loneliness and depression using the UCLA Loneliness Scale and the Geriatric Depression Scale (GDS) at Follow-up Visit 1 (FUV1). Investigate the treatment effect of immediate cochlear implantation vs continued use of HAs on physical functioning measures such as daily activity and lifestyle using the Lifestyle Activity Questionnaire (LAQ) at Follow-up Visit 1 (FUV1). To determine the effect of treating hearing loss with CI versus continued use of HAs on quality of life in each arm (immediate CI vs continued HA use) using the Health Utilities Index Mark III (HUI-III) at Follow-up Visit 1 (FUV1). To quantify pre- to post-implantation outcomes associated with cochlear implantation. 
 Self-reported hearing ability using the Hearing Handicap Inventory for the Elderly – Screening (HHIE-S). Outcomes for both the treated ear and everyday listening condition (bimodal): speech perception in quiet using CNC Words presented 60 dBA and speech perception in speech-weighted noise using AzBio sentences presented at 65 dBA using a +10 dB Signal to Noise Ratio (SNR). Investigate maintenance of treatment effect on neuropsychological, psychosocial, physical, quality of life and audiometric measures obtained at: 
 FUV2 compared to FUV1 (Arm A). FUV3 compared to FUV2 (Arm B).

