6.7.1.2 Tertiary Analyses

All tertiary analyses will be presented using descriptive statistics and analyzed using a t-test to compare the mean score of the cochlear implant Arm A to that of the hearing aid control Arm B at various time points. As these tertiary analyses are exploratory in nature, there will be no adjustment for multiple comparisons, no formal hypotheses testing and no statement of statistical significance.

Investigating treatment effect on:

- Neuropsychological outcomes:
 - Cogstate¹:
 - ☒ Detection Test – speed of performance
 - ☒ Groton Maze Learning Test – number of errors
 - ☒ Identification Test – speed of performance
 - ☒ One Card Learning Test – accuracy of performance
 - ☒ One Back Test – speed of performance
 - A6 vs B6 (treatment effect)
 - A0 vs B0 (population)
 - A6 vs B12 (6 months post-CI)
 - A12 vs B18 (12 months post-CI)
 - A0 vs A6 vs A12 (longitudinal treatment effect)
 - B6 vs B12 vs B18 (longitudinal treatment effect)
 - HI-MoCA:
 - ☒ A6 vs B6 (treatment effect)
 - ☒ A0 vs B0 (population)
 - ☒ A6 vs B12 (6 months post-CI)

¹ A sensitivity analyses will be conducted with test data integrity failures excluded if the integrity failure rate is greater than 10%.

Statistical Analysis Plan		Page 13 of 16
Sponsor	Study	CIP Version
Cochlear	Hearing Loss in Older Adults	9.0

- ☒ A12 vs B18 (12 months post-CI)
- ☒ A0 vs A6 vs A12 (longitudinal treatment effect)
- ☒ B6 vs B12 vs B18 (longitudinal treatment effect)
- Psychosocial measures:
 - UCLA Loneliness Scale:
 - ☒ A0 vs B0 (population)
 - ☒ A6 vs B12 (6 months post-CI)
 - ☒ A12 vs B18 (12 months post-CI)
 - ☒ A0 vs A6 vs A12 (longitudinal treatment effect)
 - ☒ B6 vs B12 vs B18 (longitudinal treatment effect)
 - Geriatric Depression Scale (GDS):
 - ☒ A0 vs B0 (population)
 - ☒ A6 vs B12 (6 months post-CI)
 - ☒ A12 vs B18 (12 months post-CI)
 - ☒ A0 vs A6 vs A12 (longitudinal treatment effect)
 - ☒ B6 vs B12 vs B18 (longitudinal treatment effect)
- Audiometric measures:
 - HHIE-S:
 - ☒ A0 vs B0 (population)
 - ☒ A6 vs B12 (6 months post-CI)
 - ☒ A12 vs B18 (12 months post-CI)
 - ☒ A0 vs A6 vs A12 (longitudinal treatment effect)
 - ☒ B6 vs B12 vs B18 (longitudinal treatment effect)
 - SSQ12:
 - ☒ A0 vs B0 (population)
 - ☒ A6 vs B12 (6 months post-CI)
 - ☒ A12 vs B18 (12 months post-CI)
 - ☒ A0 vs A6 vs A12 (longitudinal treatment effect)
 - ☒ B6 vs B12 vs B18 (longitudinal treatment effect)

Statistical Analysis Plan		Page 14 of 16

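### The exploratory 12- and 18-month contrasts use t-tests on available data, with pairing unstated and drop-outs' earlier scores unused for later visits, so they could be biased if drop-out is related to those scores.

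*SAP*

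**What the plan says.** **Missing data.** SAP 6.4 provides that "missing data will be handled by multiple imputation for the primary endpoint (SSQ12) with covariates of gender, age and baseline in the ITT Analyses". SAP 6.6.1 places that endpoint at FUV1. For the rest, "For all other analyses, no attempt will be made to impute missing data", and the safeguard offered is that "the number of observations available will be reported so the reader can assess the impact of missing data".

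**Late-visit analyses.** SAP 6.7.1.2 gives descriptive statistics and a t-test. The sentence describes a comparison of Arm A with Arm B at various times. The rows beneath it also include three-visit comparisons within one arm, such as "A0 vs A6 vs A12 (longitudinal treatment effect" and the Arm B counterpart at 6, 12 and 18 months. No method is stated for these: paired or unpaired, or how a t-test handles three visits. The SAP contains no repeated-measures model. The only sensitivity analysis in the section concerns Cogstate integrity failures. The section is labelled exploratory, without formal testing or statements of significance.

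**Maintenance aim.** The protocol synopsis lists maintenance of effect among the ancillary analyses: "FUV2 compared to FUV1 (Arm A", and FUV3 against FUV2 in Arm B.

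**Attrition.** SAP 4.1 states: "The randomization table will account for 20% subject attrition". It adds: "If a subject withdraws from the clinical investigation, they will be not be replaced by another subject". Neither sentence ties the 20% to a visit or an arm. SAP 5.1.1 lists "No accounting for attrition or lost to follow up" among its assumptions and then sizes the trial with 20% attrition.

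**The concern.** A mean at FUV2 or FUV3 is taken over the subjects still attending. If those who scored lower at the previous visit are more likely to leave, the later observed mean rises although nobody has changed. Restricting the comparison to subjects seen at both visits does not cure this. The low scorers who would have drifted back towards the average are gone, so the completers' mean change is pulled down.

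Maintenance is a question about a change near zero, so a modest selection effect can look like further gain or like decline. Because the SAP does not fix the pairing, the sign of any such error would depend on a choice made at analysis. The trial will already hold the baseline and earlier follow-up scores of most subjects who leave. SAP 6.4 uses the baseline score for SSQ12 at FUV1, but nothing comparable is planned for SSQ12 at FUV2 or FUV3.

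**Working it through.** **The plan's own figure.** SAP 5.1.1: d = 3.0/1.8 = 1.667, two-sided alpha 0.025, 80% power. A two-sample t-test needs 9 per arm (power 84.4%). 9/0.8 = 11.25, rounded up to 12 per arm, which matches the SAP and is not in dispute. With 60 subjects, 20% loss leaves 30 x 0.8 = 24 per arm.

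**Inputs for the bias check**
- Loss q = 0.20, from SAP 4.1. Placing all of it between two successive visits is an assumed upper case.
- Visit SD 1.8 points. This is an assumption: the SAP gives 1.8 only as the SD of change.
- Correlation r between successive visits 0.5 to 0.8 (assumed).
- Drop-outs score g = 0.85 to 2.05 points lower at FUV1 than those who stay (assumed). This corresponds to logistic drop-out on the FUV1 score with slopes of 0.5 to 1.5 per SD.
- True FUV2 minus FUV1 change: 0.

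**Formulas.** Losing the drop-outs raises the stayers' FUV1 mean by s = q x g. With a linear relation between visits, the stayers' FUV2 mean is raised by r x s. So:
- available cases (all of FUV2 against all of FUV1): error = + r x s
- paired completers: error = r x s - s = -(1 - r) x s

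**Numbers**
- s = 0.2 x 0.85 = 0.17 to 0.2 x 2.05 = 0.41 points.
- Available cases: 0.5 x 0.17 = +0.09 to 0.8 x 0.41 = +0.33.
- Paired completers: -0.2 x 0.17 = -0.03 to -0.5 x 0.41 = -0.21.
- Middle case (slope 1.0, r = 0.7): s = 0.174 SD x 1.8 = 0.31, giving +0.22 and -0.09.
- 10% loss, same g: s = 0.085 to 0.205, so +0.04 to +0.16 and -0.02 to -0.10.
- Drop-out unrelated to outcome: g = 0, so both errors are 0.

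Simulation with 30 subjects gives the same ranges. The available-case error is 0.24 to 1.1 of its standard errors. A likelihood estimate using the earlier scores is within 0.01 of zero, with standard error 0.23 to 0.37 against 0.27 to 0.38 for available cases.

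**Outer bound.** If exactly the worst 20% left, the observed mean would be off by 0.35 SD = 0.63 points.

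**Drop-out driven by the unseen FUV2 score** (slope 1.0, r = 0.5 to 0.9):

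| Estimate | Error, SD | Error, points |
|---|---|---|
| Available cases | 0.17 | 0.31 |
| Likelihood, using FUV1 score | 0.04 to 0.13 | 0.07 to 0.24 |
| Paired completers | 0.02 to 0.09 | 0.03 to 0.16 |

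**Covariance in the repeated-measures model.** At 6 months Arm A is implanted and Arm B is not, so correlations at the same calendar visit may differ by arm. A large-sample check assumed r = 0.7 to 0.8 between visits in the same implant state, 0.3 to 0.5 across implantation, and 20% loss in each arm. One unstructured covariance shared by both arms left about +0.02 to +0.10 points in Arm A and -0.02 to -0.10 in Arm B. Arm-specific covariance left about 0 (within 0.01).

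**The case against.** The strongest reply is that no bias has been shown. The documents give no drop-out pattern, and without a link between drop-out and outcome the error is zero. A reader might infer that the 12- and 18-month results will be biased; the documents support only that they could be.

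Other tempting readings also go too far:
- **That 20% will be missing by a given visit.** It is an allowance for the whole trial.
- **That the plan commits to comparing whoever attends each visit.** The t-test sentence describes Arm A against Arm B, and pairing within an arm is simply unstated.
- **That not imputing is the fault.** A likelihood model without imputation gives about zero error when drop-out depends on observed scores.
- **That every non-primary analysis is affected to this extent.** The 6-month comparisons of the arms were not sized here. Part of the difference between A12 and B18 is design: Arm B reaches 12 months of implant use at its 18-month visit.

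Consequence is also limited. These rows are exploratory, the observed n is reported, and SAP section 7 lets missing data justify a documented change. Even the largest simulated error, 0.33, is 11% of the assumed change of 3.0.

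The remedy has limits too. When drop-out depends on unseen scores the model is still off, and in that check paired completers came closer to zero.

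All of this stands and narrows the point without removing it. An n by visit gives the reader neither the direction nor the size of any error, and 3.0 is not the yardstick for a maintenance change near zero. An unstated pairing whose two readings err in opposite directions should be settled before the data are seen.

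**Conclusion.** The point holds for the exploratory 12- and 18-month longitudinal and maintenance contrasts. They rest on available-data t-tests with unstated pairing and no missing-data sensitivity analysis. They could be off by about +0.1 to +0.3 SSQ12 points (available cases) or -0.03 to -0.2 (paired completers), and by roughly half that at 10% loss. These sizes depend on the assumed visit SD, correlations and drop-out gap, and on placing all 20% attrition in one interval. Only SSQ12 was sized; the other outcomes share the mechanism, but the documents give no figures for them. The primary FUV1 analysis is unaffected. This is a low-cost improvement to a stated method and does not threaten the trial's main conclusion.

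**What to change.** In SAP 6.7.1.2, with a cross-reference in 6.4, for each outcome collected at three or more visits:

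1. Replace the t-tests with a mixed model for repeated measures on all observed visits: arm, visit and arm-by-visit interaction, REML, Kenward-Roger degrees of freedom.
2. Estimate an unstructured covariance separately by arm, or fit one model per arm, because implant status at a given visit differs between arms. Name a simpler fallback structure in case of non-convergence.
3. Read the planned within-arm and between-arm rows as contrasts with 95% confidence intervals. This also settles the pairing question.
4. Keep the table of n by visit, and keep the exploratory label.
5. Add a short sensitivity analysis for drop-out that depends on unobserved scores, for example shifting drop-outs' predicted later scores down by a stated range.

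Cost: SAP wording and some programming in the SAS 9.4 already named, with no new data, visits or subjects. Downsides: the main model assumes data are missing at random, and arm-specific unstructured covariances may not converge with about 24 to 30 subjects per arm.
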